1. PURPOSE OF THE STUDY

a. Brief Summary

This project aims to evaluate the use of Virtual Reality (VR) based visual stimulation for the treatment of blindness arising from Glaucoma and other retinal diseases or disorders of the visual system, through regeneration of axons of retinal ganglion cells (RGCs) in humans. In certain cases of blindness, such as in Glaucoma, or in certain injuries, the optic nerves behind the retina of our eyes get damaged, leading to partial blindness, mostly near the periphery of our eye. Recent research in [name] laboratory has identified visual stimulation as a non-invasive model for regeneration of such damaged axons in rodents, back to the vision centers of their brain.

b. Objectives

This project will help us to evaluate the feasibility of using virtual reality-based approaches for retinal regeneration in humans with glaucoma, retinal diseases or other optic injuries. We will use Best corrected visual acuity, Humphrey visual field test, Ocular Coherence Tomography to evaluate functional and structural changes and the National Eye Institute's visual functional questionnaire (VFQ-25).

c. Rationale for Research in Humans

The purpose of the study is to evaluate the effect of VR based stimulation on patients with glaucoma, other retinal diseases or disorders of the visual system and subjects with normal vision.

2. STUDY PROCEDURES

a. Procedures

Screening visit will include eye exam, best corrected visual acuity (BCVA), Humphrey visual field test (HVF), and Ocular Coherence Tomography (OCT), all these tests will be performed as standard of care. Baseline visit will include HVF and VFQ25. VFQ25 could be also applied at screening visit. After subject complete Screening and Baseline visit within 8 weeks, the subject will be trained on how to do VR stimulation. And will be provided a VR headset to take home. The VR or VR stimulation will consist in up to 1 hour per day session that will be done at home Monday through Friday for 12 weeks and the following week BCVA, HVF will be performed. The following week the study subject will start another cycle of 12 weeks of VR stimulation and the following week, will repeat test (BCVA, HVF) and so until the study subject complete up to 8 cycles. At

least 8 weeks after completing the last cycle subject will do HVF, OCT, BCVA and VFQ25. VR 1-hour sessions will consist of an exposure to a non-invasive visual stimulation where the subject will be sitting wearing a VR headset. After subjects complete 52 weeks of VR stimulation (4 cycles) they will be able to continue for another 52 weeks (4 cycles), or stop the VR stimulation and we will follow them doing only the testing (Visual acuity, Visual field test, OCT) every 12 weeks for another 12 months. The VR or VR stimulation will be performed as part of research, at no cost, HVF, OCT an eye exam will be considered standard of care and billable to subject insurance.

b. Procedure Risks

The VR stimulation is a designed computational model developed by Stanford University researchers, this model aims to maximize the activity of the neurons in the retina, and it will pose no more than minimal risks involved with using any of the currently commercially available Virtual Reality platforms, such as the Oculus Rift (<https://www3.oculus.com/en-us/rift/>), or the HTC Vive (<https://www.amazon.com/HTC-VIVE-Virtual-Reality-System- Pc/dp/B00VF5NT4I>), or the magic leap's system (<https://www.magicleap.com/>). BCVA, HVF and OCT tests are currently performed at the clinic for regular patient care, and will be used to measure any structural or functional change. The VFQ-25 will also tell us if there is any significant impact in the quality of life/vision of the study subjects.

c. Use of Deception in the Study

No deception will be used.

d. Use of Audio and Video Recordings

No audio or video recording will take place.

e. Alternative Procedures or Courses of Treatment

There are alternative treatments available for glaucoma including drug therapy and surgery that are used to reduce the intraocular pressure. Participants will be able to continue their current glaucoma treatment during their participation in the study and get any of these treatments as needed.

f. Will it be possible to continue the more (most) appropriate therapy for the participant(s) after the conclusion of the study?

Yes

g. Study Endpoint(s)

Primary and secondary efficacy endpoints will be measured by:

-Change in visual field by any one of the following three indices:

1. Visual Field Index(VFI)
2. Meand Deviation (MD)
3. Pointwise linear regression (PLR) analysis

-Change in the OCT: retinal nerve fiber layer (RNFL), change in ganglion cell layer, changes in other retina cell layers

3. BACKGROUND

a. Past Experimental and/or Clinical Findings

Recently, a groundbreaking paper came out from the Huberman lab (Lim, J. H. A., Stafford, B. K., Nguyen, P. L., Lien, B. V., Wang, C., Zukor, K., ... & Huberman, A. D. 2016. *Neural activity promotes long-distance, target-specific regeneration of adult retinal axons*. *Nature Neuroscience*) identifying biased visual stimulation as an independent non- invasive modality for retinal regeneration in animal models. They also found that the effects of the visual stimulation were mediated through spiking in the retinal-ganglion cells in the animal models. Also, very recently, Gall et al. (Gall, C., Schmidt, S., Schittkowski, M. P., Antal, A., Ambrus, G. G., Paulus, W., ... & Lux, A. 2016. *Alternating current stimulation for vision restoration after optic nerve damage: a randomized clinical trial*. *PLoS one*, 11(6), e0156134) has reported a mean improvement of 24% in the visual field when they applied repetitive transorbital alternating current stimulation to partially blind patients (optic nerve damage). Earlier, EJ Chichilnisky's research (Pillow, J. W., Shlens, J., Paninski, L., Sher, A., Litke, A. M., Chichilnisky, E. J., & Simoncelli, E. P. 2008. *Spatio-temporal correlations and visual signalling in a complete neuronal population*. *Nature*, 454(7207), 995-999) has identified a model for generating stimulus leading to correlated spiking activity across a complete population of parasol RGCs in macaques. Matsuura et al. (Matsuura, M., Hirasawa, K., Murata, H., & Asaoka, R. 2015. *The Relationship Between Visual Acuity and the Reproducibility of Visual Field Measurements in Glaucoma Patients*. *VA and Visual Field Measurement Reproducibility IOVS. Investigative ophthalmology & visual science*, 56[9], 5630- 5635) recently reported that reproducibility of visual field tests becomes poor with the deterioration of visual acuity, suggesting a relation between the two. A couple key animal studies have led to the formulation of this project, which we mention below.

b. Findings from Past Animal Experiments

Recently, a groundbreaking paper came out from the Huberman lab (Lim, J. H. A., Stafford, B. K., Nguyen, P. L., Lien, B. V., Wang, C., Zukor, K., ... & Huberman, A. D. 2016. *Neural activity promotes long-distance, target-specific regeneration of adult retinal axons*. *Nature Neuroscience*) that identified biased visual stimulation as an independent non- invasive modality for retinal regeneration in animal models. They also found that the effects of the visual stimulation were mediated through spiking in the retinal-ganglion cells in the animal models. A recent paper in animal models (Baden, T., Berens, P., Franke, K., Rosón, M. R., Bethge, M., & Euler, T. 2016. *The functional diversity of retinal ganglion cells in the mouse*. *Nature*, 529(7586), 345-350) has used a series of visual stimulation (chirp, moving bars, noise and color), leading to activation (through spiking) of more than 30 functional output channels in the mouse retina. Earlier, EJ Chichilnisky's research has identified a model for generating stimulus leading to correlated spiking activity across a complete population of parasol RGCs in macaques.

We plan to tailor our visual stimulation based on these models.

4. DEVICES USED IN THE STUDY

a. Investigational Devices (Including Commercial Devices Used Off-Label)

Investigational Device 1	
Name:	Virtual Reality software
Significant Risk? (Y/N)	No

5. DRUGS, BIOLOGICS, REAGENTS, OR CHEMICALS USED IN THE STUDY

a. Investigational Drugs, Biologics, Reagents, or Chemicals

N/A

b. Commercial Drugs, Biologics, Reagents, or Chemicals

Commercial Product 1	
Name:	Proparacaine Hydrochloride
Dosage:	0.5%
Source	Byers Eye Institute Clinic
Commercial Product 2	
Name:	Tropicamide
Dosage:	0.5%
Source	Byers Eye Institute Clinic
Commercial Product 3	
Name:	Phenylephrine
Dosage:	2.5%
Source	Byers Eye Institute Clinic

6. PARTICIPANT POPULATION

a. Planned Enrollment

200 subjects with glaucoma or other retinal diseases or disorders of the visual system 100 normal controls (patients with normal vision) General population, above the age of 12, willing to take part in our study, with glaucoma or other retinal diseases or disorders of the visual system or normal controls. All subjects will be recruited at Byers Eye Institute Stanford University

b. Age, Gender, and Ethnic Background

Age >12 both sexes will be recruited. Any ethnic background.

c. Vulnerable Populations

No potentially vulnerable subjects will be actively recruited into this study.

d. Rationale for Exclusion of Certain Populations

Children 12 years old and older will be included in the study. Current VR systems have proven to be safe on children 12 years and older.

e. Healthy Volunteers

100 patients with normal vision (healthy volunteers) will be recruited for the study, as long as they satisfy screening, inclusion and exclusion criteria.

The participants will be exposed to no more than minimal risk, associated with watching media on currently commercially available Virtual Reality platforms, such as the Oculus Rift (<https://www3.oculus.com/en-us/rift/>), or the HTC Vive (<https://www.amazon.com/HTC-VIVE-Virtual-Reality-System-Pc/dp/B00VF5NT4I>), or the magic leap's system (<https://www.magicleap.com/>). Additionally, to protect the welfare of the participants, they will be clearly told in the informed consent, which they will sign before entering the study, that they are free to discontinue at any point if they want.

f. Recruitment Details

Participants will be identified from the Stanford Healthcare clinic population at the Byers Eye Institute at Stanford who meet the inclusion criteria. Participants who are identified during chart review will be notified of their eligibility, after the patient's physician has previously notified the potential research participant and obtained approval to be contacted.

g. Eligibility Criteria

i. Inclusion Criteria

For subjects with glaucoma, other retinal diseases, or disorders of the visual system:

1. Patient age > 12 years
2. Compliance with investigator instructions, tests and visit during subject participation in the study.
3. Sufficient fixation ability
4. Best corrected visual acuity of 20/200 or better in at least one eye, or capable to see the visual stimulus at least in one eye.

For healthy volunteers:

1. Patient age > 12 years
2. Compliance with investigator instructions, tests and visit during subject participation in the study.
3. Best corrected visual acuity of 20/20 in both eyes.
4. Sufficient fixation ability

ii. Exclusion Criteria

1. Electric or electronic implants (such as cardiac pacemaker)
2. Any metal artifacts in the head or truncus area (with the exception of dental implants)
3. Epilepsy and photo-sensitivity; acute auto-immune diseases
4. Acute conjunctivitis
5. Pathological nystagmus

h. Screening Procedures

All screening test will be performed at the ophthalmology clinic, pre-screening of potential subjects will be done through Epic system.

i. Participation in Multiple Protocols

As part of the consent process, potential subjects will be asked if they are participating in any other studies. Participating in other studies will not be an exclusion criteria to participate in this study.

j. Payments to Participants

Subjects will not be paid.

k. Costs to Participants

The VR stimulation sessions will not have any cost to the participants, all other procedures (Eye exam, visual field, OCT) will be billable to patient insurance as standard of care, patient will be responsible of any copays.

l. Planned Duration of the Study

The estimated active participation of the study subjects is 24 months.

Screening visit may take about 2-3 hours

The data analysis of all study participants will be approximately 6-8 years.

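### Does the alternative route in the acuity criterion let in eyes whose visual fields are too unreliable for the efficacy endpoint?

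*Protocol*

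**What the plan says.** Inclusion criterion 4 for patients (Protocol 6.g.i) requires "Best corrected visual acuity of 20/200 or better in at least one eye, or capable to see the visual stimulus at least in one eye". The same list asks for "Sufficient fixation ability" and for compliance with the study tests and visits. Section 6.g.ii excludes "Pathological nystagmus". No lower acuity limit appears elsewhere for patients. Healthy volunteers must have "Best corrected visual acuity of 20/20 in both eyes".

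The background (3.a) cites a study in glaucoma patients that "recently reported that reproducibility of visual field tests becomes poor with the deterioration of visual acuity, suggesting a relation between the two". Section 2.g lists, under a joint heading for primary and secondary efficacy endpoints, "Change in visual field by any one of the following three indices" (VFI, MD or pointwise linear regression), followed by OCT measures. It names no study eye.

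Planned patient enrolment (6.a) is "200 subjects with glaucoma or other retinal diseases or disorders of the visual system". Section 1 gives the aim as treating blindness from glaucoma and other retinal or visual-system disorders, and the objective as assessing feasibility.

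**The concern.** A numerical limit followed by *or* and a softer condition invites suspicion. A patient worse than 20/200 in both eyes still enters if one eye can see the stimulus, and no test or threshold for seeing it is given. The figure 20/200 therefore looks decorative.

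The background then says that fields are less reproducible when acuity is poor, and field change is an efficacy endpoint. Read together, the protocol seems to admit the very eyes that its own evidence warns about. The criterion also needs only one eye, so the fellow eye may have any acuity.

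If this were a real defect, extra test-retest noise would enter VFI, MD and pointwise regression. A true effect would be harder to detect, and chance gains would be larger in the noisier eyes.

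**Working it through.** **1. Logic of criterion 4.** Let A be 20/200 or better in at least one eye, and B be seeing the stimulus with at least one eye.

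| A | B | Criterion met |
|---|---|---|
| yes | yes | yes |
| yes | no | yes |
| no | yes | yes |
| no | no | no |

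Only the last row fails. The acuity figure does not bind for anyone who can see the stimulus. That part of the observation is right. The further step, that the figure has no function at all, assumes that everyone at 20/200 can see the stimulus. The protocol does not specify the stimulus well enough to settle this. If some cannot, the second row shows the acuity clause admitting people whom the stimulus clause alone would not.

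**2. Is there a contradiction?** The background statement is a gradient: reproducibility falls as acuity falls. It gives no cut-off, does not mention 20/200, and is not offered as a reason for any eligibility rule. A broad entry rule does not contradict it. Nor does it show that fields are sound above 20/200 and unsound below.

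**3. How large could the effect be?** The protocol gives no SD, effect size, power or acuity mix, so there is no planned figure to reproduce. The inputs, all assumed except n = 200 (6.a), are:

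- one eye per patient and a simple mean of MD change;
- SD of change 2 dB in eyes at 20/200 or better;
- a share f of worse eyes, with SD k times as large.

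Formulas:

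- All eyes, unweighted: variance = 4[(1 − f) + f k²], SE = √(variance/200).
- Only eyes at 20/200 or better: SE = 2/√(200(1 − f)).
- All eyes, inverse-variance weighted: effective n = 200(1 − f) + 200f/k².

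Results:

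- f = 0.2, k = 2: variance = 4(0.8 + 0.8) = 6.4. SE for all eyes = √(6.4/200) = 0.179; restricted SE = 2/√160 = 0.158. Effective n is 200/1.6 = 125 unweighted, 160 restricted, and 160 + 40/4 = 170 weighted.
- f = 0.3, k = 1.5: variance = 4(0.7 + 0.675) = 5.5. SE for all eyes = √(5.5/200) = 0.166; restricted SE = 2/√140 = 0.169. Restriction loses slightly.
- f = 0.3, k = 3: effective n = 200/3.4 = 59 unweighted, 140 restricted, and 140 + 60/9 = 147 weighted.

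Restriction beats the unweighted analysis only if k² > (2 − f)/(1 − f), that is k above 1.45, 1.50 and 1.56 for f = 0.1, 0.2 and 0.3. Weighting always beats restriction in precision, since 200f/k² is positive, provided the effect is the same in both groups of eyes and k is adequately known.

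**4. Would a narrower criterion cure it?** Replacing *or* by *and* would remove patients below 20/200 in both eyes, who belong to the group named in section 1. It would still require only one qualifying eye, so a fellow eye of any acuity could still be tested.

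**The case for a change.** The strongest case for a defect is that eligibility belongs in the protocol and no SAP can make a non-binding limit bind. The other filters do not set an acuity floor: the fixation requirement is undefined, and the nystagmus exclusion concerns eye movement. The healthy-volunteer rule shows that the protocol can state a firm acuity limit when it wants one. Separating who may enter from which eyes count for the field endpoint would need one sentence, and acuity is already measured at screening.

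Some of this stands. The acuity figure adds little, and low-acuity eyes can enter and will probably be noisier. That is a consequence of broad entry, though, not a misstatement. The healthy-volunteer limit serves a different purpose, which is to define normal vision. The fixation, compliance and nystagmus rules do bear on field reliability, even though they are not acuity limits. The proposal to define an evaluable set of eyes concerns the analysis population, which a protocol commonly leaves to the SAP; none was available here.

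The point about chance gains is weaker. Noise produces chance losses as well as gains. Apparent improvement would become more frequent under a rule counting gains beyond a fixed threshold, but section 2.g states no such threshold. The choice among three indices is a separate question from acuity.

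**Conclusion.** The concern does not hold. Criterion 4 is permissive, and its acuity figure does not bind for patients who can see the stimulus. That is a coherent way to enrol for a visual-stimulation feasibility study in people with severe sight loss, and it conflicts with nothing the protocol says about field reproducibility.

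The possible cost is imprecision; bias in a given direction is not shown. Its size rests wholly on assumed values. Against an unweighted analysis of all eyes, restricting the field analysis helps when the SD of change in low-acuity eyes exceeds about 1.5 times that in the others, and below that it costs precision. Where it helps, weighting can do better without dropping anyone: effective n of 170 against 160 at f = 0.2 and k = 2. The choice is therefore a design preference with costs on both sides. Rules for the analysed eye, field reliability and the evaluable set may stand in the SAP, so their absence from the protocol is not an error.

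### Section 6.i admits patients who are in any other study, so another trial's eye treatment could be read as a VR effect, in either direction, with no concurrent untreated patient group to reveal it

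*Protocol*

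**What the plan says.** Section 6.i has two sentences on this. The first says: "As part of the consent process, potential subjects will be asked if they are participating in any other studies". The second sets the rule: "Participating in other studies will not be an exclusion criteria to participate in this study". The rule has no limit by type of study, and none of the five exclusion criteria in section 6.g mentions another investigational treatment. The section states no use of the answer given at consent, and no rule for a patient who joins another study during the 24 months of participation estimated in section 6.l.

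Section 2.a gives VR to subjects without distinction by group: "After subject complete Screening and Baseline visit within 8 weeks, the subject will be trained on how to do VR stimulation". Section 6.a plans 200 patients and 100 normal controls. Section 1.c includes the latter among those treated; it gives this purpose: "evaluate the effect of VR based stimulation on patients with glaucoma, other retinal diseases or disorders of the visual system and subjects with normal vision". After 52 weeks of VR, the choice for the next 12 months is to go on, "or stop the VR stimulation and we will follow them doing only the testing (Visual acuity, Visual field test, OCT) every 12 weeks".

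Section 2.g defines efficacy by "Change in visual field by any one of the following three indices", namely the Visual Field Index, the mean deviation (MD) or pointwise linear regression, and by change in OCT layers.

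**The concern.** Where patients are randomised to VR or a control, co-enrolment in other trials tends to balance between the arms and mainly adds noise. Here nothing balances it. The efficacy measures are changes within patients. If some of those patients are also receiving a treatment that acts on the visual field or the retinal layers, its effect becomes part of the change observed under VR.

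A helpful co-treatment could create or enlarge an apparent benefit. A harmful one could hide a real benefit. An adverse event in such a patient would also be harder to assign to VR or to the other treatment. Section 6.a recruits everyone at one eye institute and follow-up is long, so some overlap with other eye trials is plausible, but the protocol gives no estimate of it.

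**Working it through.** **Is there a comparison that would separate the two effects?** The protocol offers three candidates.
- *The 100 normal controls.* They have normal vision (section 6.g requires 20/20 in both eyes) and are themselves studied for the effect of VR (section 1.c). They are not untreated patients.
- *The testing-only year.* It follows 52 weeks of VR and is chosen by the subject (section 2.a). It is neither concurrent nor allocated.
- *A sham, delayed-start or untreated patient group.* None is described.

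So a change in a co-enrolled patient cannot be divided between VR and the other treatment.

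**How large could the distortion be?** The protocol states no effect size, SD, significance level or overlap, so there is no figure of its own to reproduce. What follows is an illustration.

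Input from the protocol: n = 200 patients (section 6.a).

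Assumptions:
- the SD of MD change is 2 dB;
- the true VR effect is zero;
- a share q of patients is in another study, and its treatment moves MD by d = 1 to 1.5 dB in every one of them;
- the test is a two-sided one-sample t-test at 5%, with 199 degrees of freedom.

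Formulas:
- spurious mean change = q × d;
- noncentrality = q × d × √200 / 2;
- rejection rate = probability that a noncentral t with that noncentrality falls outside ±1.972.

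Example: q = 0.10 and d = 1 give a mean change of 0.10 dB, a noncentrality of 0.10 × 14.142 / 2 = 0.707, and a rejection rate of 10.8%.

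| Overlap q | Patients of 200 | Spurious mean change (dB) | Noncentrality | Rejection rate (nominal 5%) |
|---|---|---|---|---|
| 2% | 4 | 0.02 to 0.03 | 0.14 to 0.21 | 5.2% to 5.5% |
| 5% | 10 | 0.05 to 0.075 | 0.35 to 0.53 | 6.4% to 8.2% |
| 10% | 20 | 0.10 to 0.15 | 0.71 to 1.06 | 10.8% to 18.4% |
| 20% | 40 | 0.20 to 0.30 | 1.41 to 2.12 | 29% to 56% |

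**Two checks on the assumptions.**
- Mixing shifted and unshifted patients raises the SD to √(4 + q(1 − q)d²). At q = 0.20 and d = 1.5 this is √(4 + 0.16 × 2.25) = 2.088, and the rejection rate falls from 56% to 52%. At 10% overlap or less the rate changes by less than one percentage point.
- If half of the co-enrolled patients receive an inactive comparator, the mean shift halves. At 10% overlap and d = 1 it is 0.05 dB, and the rejection rate is 6.4%.

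A downward shift of the same size gives the same rejection rates in the direction of harm.

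**The case against.** The strongest objection is that the root problem lies elsewhere. Attribution fails because patients have no concurrent control. Section 2.e also lets participants continue their glaucoma treatment and receive further treatment as needed, which may affect more patients than co-enrolment does. This stands as a limit on what amending 6.i can achieve. It does not excuse the rule: trial co-enrolment can be restricted without withholding standard care.

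A second objection is that the risk is conditional. This also stands. A reader might infer from 6.i that other treatments' effects will be counted as VR benefit. The protocol does not support that: it gives no overlap and no effect, and the effect could run downward. A reader might likewise infer that adverse events could not be attributed at all. That goes too far, since section 7.d places adverse events under review and they can be judged case by case.

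A third objection is that the bias cannot be called large and the loss of recruits small at once. That is right. Both rise with the overlap, as the table shows.

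A fourth is that the analysis may be settled in the statistical analysis plan, which is not at hand, and that section 1.b speaks of feasibility. An analysis plan can indeed set how co-enrolled patients are handled. It cannot change who is eligible, and it can use only what is collected. The protocol asks about other studies only at consent, and section 2.g lists efficacy endpoints despite the feasibility aim.

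**Conclusion.** The point holds as a conditional risk that comes from a stated rule. Section 6.i admits patients from interventional eye trials, and the design as described cannot separate another treatment's effect from that of VR.

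The size is unknown. Under the assumptions above, a few per cent of overlap does little: the rejection rate is about 5% to 8% at 2% to 5% overlap. It matters at 10% (11% to 18%) and is serious at 20% (29% to just over 50%). The illustration credits every co-enrolled patient with a full 1 to 1.5 dB shift, so comparator arms or opposing effects in the other studies would lower these figures.

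The rule is worth changing because the change is simple, but it is a smaller matter than the lack of a concurrent control.

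**What to change.** Amend section 6.i so that concurrent enrolment in an interventional study of an eye or visual-system treatment is an exclusion. Observational studies, such as registries and imaging studies, and non-ocular studies stay allowed. Repeat the co-enrolment question at each study visit and record the answer with its date. Report a sensitivity analysis without data collected after a patient joins such a study. Whether those data also leave the main analysis can be settled in the analysis plan.

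The cost is one amended sentence in 6.i, one question per visit, and the loss of recruits already in such studies: about 4 of 200 at 2% overlap and 40 of 200 at 20%. The question is already asked at consent, so screening for the exclusion needs no new procedure.

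In the illustration, the exclusion sets q to zero at entry, so the spurious shift from patients already co-enrolled disappears. Confounding by changes in standard glaucoma treatment (section 2.e) would remain, as would the lack of a concurrent control.
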